2 STUDY OBJECTIVES

2.1 Primary Objective

Aim 1a. Investigate the feasibility of a clinical trial administering ionizing radiation with concurrent CR for the treatment of breast cancer. True adherence will be defined as a successful reduction of 25% of total calories based on diet journals in at least 80% of the logged events.

Aim 1b. Acute skin toxicity as defined by the National Cancer Institute Common Toxicity Criteria (NCI CTCv.4 for skin reaction, pain and the occurrence of moist desquamation) will be followed to ensure noninferiority as compared with historical controls.

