3.4 Primary Safety Endpoints

Acute toxicities will be evaluated by the CTCAE, Version 4.0. (<http://ctep.info.nih.gov>). If a patient has a serious adverse event such as all unexpected hospitalizations and all grade 4 and 5 SAEs, the patient will be removed from the trial. See Appendix III for scale.

4 Subject Selection and Withdrawal

Patients must have baseline evaluations performed prior to the first dose of study drug and must meet all inclusion and exclusion criteria. Results of all baseline evaluations will be reviewed by the Principal Investigator prior to enrollment, to verify that all inclusion and exclusion criteria have been satisfied. In addition, the patient must be thoroughly informed about all aspects of the study, including the study visit schedule and required evaluations and all regulatory requirements for informed consent. The written informed consent must be obtained from the patient prior to screening procedures being performed. The following criteria apply to all patients enrolled onto the study unless otherwise specified.

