6.2.3 Phase II—Visits During Radiation Treatment

Visit 4-9: Patients will be monitored for acute radiation toxicity including skin changes and desquamation. Patients will be questioned and examined to ensure general health and will be reassured about radiation-related side effects. Patients will turn in their food diary from the previous week and dietary counselors will review these with the patients to determine how they can continue to comply with dietary modification. At each visit, a 24hr recall of diet will be asked of the patient and compared with the diet journal to determine the self reporting accuracy. Each week during this period, patients will be counseled on their diet and given behavioral modification lessons corresponding to specific weeks in the diet (see Appendix V for worksheets). Weight will be taken at weeks 3, 5 and 7 of the diet, corresponding to weeks 1, 3 and 5 of radiation and vital signs will be performed weekly. FACT-B psychosocial assessment will be given at visit 7 along with the PROMIS cancer fatigue short form. In addition, at visit 7 (week 5 of diet) patients will have a fasting blood draw done for insulin level.

Radiation will be planned to be administered 5 days a week, Monday through Friday. Radiation is given for approximately 6-6.5 weeks or 30-33 treatments.

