6.6 Radiation Therapy Adverse Events

All Radiation Therapy AEs will be scored according to the NCI Common Terminology Criteria for Adverse Events (CTCAE) version 4

Short Term: Fatigue is an anticipated systemic reaction to radiation treatment. Skin erythema, desquamation, breast edema, breast tenderness and myositis are potential local reactions.

Long Term: Long term effects possibly include radiation pneumonitis, rib fractures, second malignancy and for left-sided lesions cardiac complications

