8.5.1 Medical Monitoring and AE/SAE Reporting

A Medical Monitor is assigned to this study at the Thomas Jefferson University. This is a physician/pharmacist who is not directly involved in the trial, and is not currently collaborating with the sponsor/investigator on any other trial. The role of the Medical Monitor is to review all reportable AEs/SAEs (in real-time) including grading, toxicity assignments, non-reportable AEs (quarterly), protocol violations/deviations, as well as all other safety data and activity data observed in the ongoing clinical trial occurring at Thomas Jefferson University. The Medical Monitor may recommend reporting of adverse events and relevant safety data, and may also recommend suspension or termination of the study to the DSMC and TJU IRB.

Every KCC investigator initiated protocol includes requirements for reporting of adverse events based on CTC 4.0. All events are reported to the IRB and Medical Monitor using a password protected web-site. In addition all unexpected and serious adverse events (SAEs) are reported to the TJU IRB and to the Food and Drug Administration (FDA) if applicable. The investigator is required to submit all unexpected and serious adverse events to the TJU IRB and the Medical Monitor within the timeframes outlined in the below table. All AE/SAEs will be reported to

the DSMC at the quarterly DSMC review meetings; however, if the Medical Monitor determines corrective action is necessary, an “ad hoc” DSMC meeting will be called. **Fatal adverse events related to treatment which are unexpected must be reported within 24 hours to the TJU IRB and the DSMC. Fatalities not related to the study drug/device must be reported within 5 days.** A summary of the reporting requirements for KCC investigator initiated Phase I and Phase II studies are presented below.

	Grade 1	Grade 2	Grade 2	Grade 3		Grade 3		Grades 4 and 5
	Unexpected and Expected	Unexpected	Expected	Unexpected with Hospitalization	Unexpected without Hospitalization	Expected with Hospitalization	Expected without Hospitalization	Unexpected and Expected
Unrelated Unlikely	Reviewed at Quarterly DSMC Meeting and IRB Annual Review	Reviewed at Quarterly DSMC Meeting and IRB Annual Review	Reviewed at Quarterly DSMC Meeting and IRB Annual Review	5 Working Days	Reviewed at Quarterly DSMC Meeting and IRB Annual Review	5 Working Days	Reviewed at Quarterly DSMC Meeting and IRB Annual Review	Phase 1 - 48 Hours (Death: 24 Hours) Phase 2 - 5 Working Days

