 - Chronic Diarrhea or Vomiting
 - Active Eating Disorder
- Currently using steroids
-
- Active/history of substance abuse or dependency to include prescription or illicit drugs as well as alcohol.
- Decisionally impaired patients.

Checklist for Screening Visit:

Informed Consent for Trial Obtained	
All Sections of CRF Completed	
Inclusion/Exclusion Criteria Evaluated	
Blood draw: Beta-HCG	
H&P; Performance Status	
Weight, BMI	
Based on screening patient appears eligible	

CAREFOR Study Case Report Form (CRF)—Radiation Treatment Planning Visit

Date of Sim Visit: _____

Lumpectomy Details

Please indicate the actual date of the lumpectomy, whether or not there were any post-op complications and the status of the Path report:

Surgery DatePre-op DiagnosisPost-Op Complications_____

Path Report Received? Y or N

Attach a copy of the Path Report to this visit.

Verify Allergies:_____

_____**Changes to Current Medications (indicate dose, route, frequency and start date):**

Medication

Dose

Route

Frequency

Start Date

Physical Examination

Height: _____ Weight: _____ BMI: _____
 Vital Signs: BP: _____ HR: _____ Temp: _____ RR: _____
 Caliper Measurements: _____

Bioimpedance Measurement: _____

Please indicate the status (normal or abnormal) of each system listed below. If abnormal, please make notes. Give detailed description of breast exam in the notes section.

Organ System	Status	Notes
CVS	Normal Abnormal	_____
Pulm	Normal Abnormal	_____ _____
GI	Normal Abnormal	_____ _____
Neuro	Normal Abnormal	_____ _____
Breast	Normal Abnormal	_____ _____ _____

CTCAE v4.0 Evaluation

Please evaluate the patient at baseline for comparison during and post-radiation.

Adverse Event	Grade				
	1	2	3	4	5
Dermatitis radiation	Faint erythema or dry desquamation	Moderate to brisk erythema; patchy moist desquamation, mostly confined to skin folds and creases; moderate edema	Moist desquamation in areas other than skin folds and creases; bleeding induced by minor trauma or abrasion	Life-threatening consequences; skin necrosis or ulceration of full thickness dermis; spontaneous bleeding from involved site; skin graft indicated	Death
Definition: A finding of cutaneous inflammatory reaction occurring as a result of exposure to biologically effective levels of ionizing radiation.					
Skin hyperpigmentation	Hyperpigmentation covering <10% BSA; no psychosocial impact	Hyperpigmentation covering >10% BSA; associated psychosocial impact	-	-	-

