Edema	Yes	No	

CTCAE v4.0 Evaluation

Adverse Event	Grade				
	1	2	3	4	5
Dermatitis radiation	Faint erythema or dry desquamation	Moderate to brisk erythema; patchy moist desquamation, mostly confined to skin folds and creases; moderate edema	Moist desquamation in areas other than skin folds and creases; bleeding induced by minor trauma or abrasion	Life-threatening consequences; skin necrosis or ulceration of full thickness dermis; spontaneous bleeding from involved site; skin graft indicated	Death
Definition: A finding of cutaneous inflammatory reaction occurring as a result of exposure to biologically effective levels of ionizing radiation.					
Skin hyperpigmentation	Hyperpigmentation covering <10% BSA; no psychosocial impact	Hyperpigmentation covering >10% BSA; associated psychosocial impact	-	-	-
Definition: A disorder characterized by darkening of the skin due to excessive melanin deposition.					
Fatigue	Fatigue relieved by rest	Fatigue not relieved by rest; limiting instrumental ADL	Fatigue not relieved by rest, limiting self care ADL	-	-
Definition: A disorder characterized by a state of generalized weakness with a pronounced inability to summon sufficient energy to accomplish daily activities.					

Checklist for Visit:

All Sections of CRF Completed	

FACT-B (Version 4)

Below is a list of statements that other people with your illness have said are important. Please circle or mark one number per line to indicate your response as it applies to the past 7 days.

PHYSICAL WELL-BEING		Not at all	A little bit	Some- what	Quite a bit	Very much
GP1	I have a lack of energy	0	1	2	3	4
GP2	I have nausea	0	1	2	3	4
GP3	Because of my physical condition, I have trouble meeting the needs of my family	0	1	2	3	4
GP4	I have pain	0	1	2	3	4
GP5	I am bothered by side effects of treatment	0	1	2	3	4
GP6	I feel ill	0	1	2	3	4
GP7	I am forced to spend time in bed	0	1	2	3	4

SOCIAL/FAMILY WELL-BEING		Not at all	A little bit	Some- what	Quite a bit	Very much
GS1	I feel close to my friends	0	1	2	3	4
GS2	I get emotional support from my family	0	1	2	3	4
GS3	I get support from my friends	0	1	2	3	4
GS4	My family has accepted my illness	0	1	2	3	4
GS5	I am satisfied with family communication about my illness	0	1	2	3	4
GS6	I feel close to my partner (or the person who is my main support)	0	1	2	3	4

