CAREFOR Study**

Current Medication Flowsheet

Date Started	Medication	Indication	Route	Frequency	Dose	Date Stopped

Allergies:

Physician Signature: _____ **Date:** _____

Study : _____ Patient Case No. _____ Time Frame/Cycle #

(circle one): Y or N, N/A

Intermittent RT

Protocol Office AE Toxicity Flowsheet

Date AE Started	Brief Description of Event♦	Numeric Grade CTC 3.0	AEs	Attribution (Related to therapy)	AE Attribution (Potential cause)	Action (Check all that apply)	Outcome
Date:  New  F-U		 0  1  2  3  4	 AE  SAE	 Unrelated  Unlikely  Possible  Probable  Definite	 Chemotherapy  Radiation  Hormone-specify  Other _____	 none required  dose reduced*  dose held*  Adcers  IRB notified  MedWatch 3500A  Other _____	 Resolved End Date: _____  Ongoing
Date:  New  F-U		 0  1  2  3  4	 AE  SAE	 Unrelated  Unlikely  Possible  Probable  Definite	 Chemotherapy  Radiation  Hormone-specify  Other _____	 none required  dose reduced*  dose held*  Adcers  IRB notified  MedWatch 3500A  Other _____	 Resolved End Date: _____  Ongoing

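### Pain is a named part of the Aim 1b toxicity endpoint, but the CTCAE v4.0 grids on the baseline and radiation-visit forms have no row for it (cheap improvement)

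*Combined protocol and SAP*

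**What the plan says.** Section 2.1 (Aim 1b), repeated in section 3.2, makes acute skin toxicity a primary endpoint, defined by "NCI CTCv.4 for skin reaction, pain and the occurrence of moist desquamation". The secondary toxicity endpoint (sections 2.2 and 3.3) also names pain on version 4.0 and has the number of patients affected and the time to occurrence recorded.

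The scale is version 4 throughout the protocol text. Section 3.4 says "Acute toxicities will be evaluated by the CTCAE, Version 4.0", section 6.6 applies version 4 to all radiation adverse events, and section 8.5.1 refers to "requirements for reporting of adverse events based on CTC 4.0". Section 6.6 also expects local discomfort: "Skin erythema, desquamation, breast edema, breast tenderness and myositis are potential local reactions". Section 8.2 has the investigator ask about adverse events at every contact.

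The visit text in section 6.2.3 reads "Patients will be monitored for acute radiation toxicity including skin changes and desquamation", and section 6.2.4 repeats this for the later visits. Neither names pain.

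The Appendix VII form for the planning visit introduces its CTCAE v4.0 grid with "Please evaluate the patient at baseline for comparison during and post-radiation". That grid and the one on the radiation-visit form have the same three rows: radiation dermatitis, skin hyperpigmentation (grade 1 is "Hyperpigmentation covering <10% BSA; no psychosocial impact") and fatigue. The general adverse event flowsheet in the same appendix has a free-text event column and grade tick-boxes under "Numeric Grade CTC 3.0".

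Section 7.2, under the label Aim 1b, tests the proportion of patients with toxicity against a historical rate of about 80% with a margin of 10 points, by an exact binomial test.

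**The concern.** The endpoint and the forms do not match. Hyperpigmentation and fatigue, which Aim 1b does not name, each have a graded row. Pain, which Aim 1b does name, has none. A grid row makes the assessor record a grade at each visit, including a zero. A free-text log records only what someone chose to enter, so an empty log may mean no pain or no question. If pain is entered on the flowsheet, its heading invites grading on a different version from the one the endpoint specifies.

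At stake is whether a component of a primary endpoint can be reported as defined. The design is single-arm, so no concurrent control group is assessed with the same forms, and the comparison depends on the trial count and the historical count describing the same event.

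**Working it through.** **1. Where pain could be recorded.**

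| Place | Pain item? | CTC version 4 grade? |
|---|---|---|
| CTCAE v4.0 grid, planning visit (Appendix VII) | No | Not applicable |
| CTCAE v4.0 grid, radiation visits (Appendix VII) | No | Not applicable |
| Adverse event flowsheet (Appendix VII) | Free text only | Numeric grade, headed version 3.0 |
| FACT-B (baseline, week 5, conclusion, 4 weeks after) | Two items, GP4 and P2 | No; patient-reported score, 0 to 4, past 7 days |

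No end-of-diet or follow-up examination form appears in the text available, so the gap is shown for the first two forms only.

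**2. Moist desquamation, for comparison.** It lies within dermatitis grades 2 and 3, and the radiation-visit form adds a desquamation yes/no item and space to describe the breast examination. The yes/no item does not separate moist from dry, but the information has a place on the form. Pain does not.

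**3. The plan's own figure.** Inputs from section 7.2: n = 90, historical rate 0.80, margin 0.10 (so the null rate is 0.80 + 0.10 = 0.90), one-sided alpha 0.05. Let X be the number of patients with toxicity. Non-inferiority is declared when X ≤ c, where c is the largest value with P(X ≤ c | 90, 0.90) ≤ 0.05.

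- P(X ≤ 75 | 0.90) = 0.0333
- P(X ≤ 76 | 0.90) = 0.0634, above 0.05, so c = 75
- Power: P(X ≤ 75 | 0.80) = 0.8209

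The stated 82% is reproduced. The arithmetic is sound, given an event counted the same way on both sides.

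**4. How a missing pain grade reaches the count.** Section 7.2 gives no combination rule. Suppose any component counts. Then

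P(toxicity) = P(skin reaction) + P(pain and no counted skin reaction).

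Only the second term depends on pain. A patient with both is counted anyway. The documents give no figure for that term, and they do not say whether the historical rate includes it. If it does, missed pain lowers the trial count relative to the benchmark and makes passing easier. If it does not, counting pain in the trial raises the trial count and makes passing harder. The direction is therefore not known either.

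**5. Illustration only, with assumed mismatches of 0, 1 and 2 points and c fixed at 75.**

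| Assumed mismatch | Trial event wider than historical, like-for-like rate 80%: P(pass) | Trial event narrower, like-for-like rate 90%: P(false pass) |
|---|---|---|
| 0 points | 82.1% (counted rate 80%) | 3.3% (counted rate 90%) |
| 1 point | 75.3% (81%) | 6.7% (89%) |
| 2 points | 67.1% (82%) | 11.8% (88%) |

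These show how sensitive the rule is. They do not estimate any mismatch in this trial.

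**The case against.** The best defence is that the protocol text already requires the grade. Sections 2.2 and 3.3 say that skin reaction or pain will be assessed on version 4.0, section 6.6 applies version 4 to every radiation adverse event, and section 8.2 requires questioning at each contact. The list in section 6.2.3 is introduced as inclusive rather than complete, and that section also has patients questioned and examined. The flowsheet has numeric grade boxes, and its heading looks like a leftover from a generic template. FACT-B asks about pain twice.

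Most of this stands, and it rules out one reading that a reader might infer: that pain is not collected. The documents do not support that, because several routes exist. What remains is that none of them gives a version 4 grade at each visit on the forms shown.

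A reader might also infer that section 7.2 leaves toxicity unconnected to Aim 1b. It does not: the paragraph carries the Aim 1b label, and sections 2.2 and 3.3 state the intent to compare this toxicity with the historical controls. What is missing is narrower, namely the grade cut-off and combination rule for the trial count and for the 80%.

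**Conclusion.** The point holds as a mismatch between endpoint and form. Followed as written, the baseline and radiation-visit grids give no systematic version 4 grade for pain, and the one other graded form carries the wrong version number. If any component counts, the effect on the tested proportion is confined to patients with pain and no counted skin reaction; its size and direction cannot be obtained from the documents.

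It would go too far to conclude that the non-inferiority test is biased or that the 82% power is wrong. The power reproduces exactly, and no mismatch between trial and historical counts has been shown. The documents only leave the common basis unstated.

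This is a cheap improvement rather than a flaw in the design. It assumes that the two forms shown are the ones in use and that no separate follow-up examination form supplies the missing row.

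**What to change.** 1. Add a CTCAE v4 pain row to the toxicity assessment at the existing visits, with a grade recorded each time, including zero. A moist desquamation yes/no item is an optional addition.
2. Change the version in the flowsheet heading to CTCAE 4.0.
3. Report how many patients were assessed on the form without the pain row.
4. In section 7.2, state the grade cut-off and the rule for combining skin reaction, pain and moist desquamation into one patient-level event, and state how the historical rate of about 80% was counted, so that both use the same event. This should be written before the toxicity data are analysed.

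The cost is a small case report form revision, one corrected heading, a short addition to section 7.2 and a look-up of how the historical rate was obtained. No visits are added. The downside is that patients already assessed will have no pain row, which item 3 discloses.

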2.2 Secondary Objective

Investigate measurable changes of patient characteristics and tissue and serum from fasting/CR conditions to determine a metric for evaluating this treatment in future studies.

[figure not shown]
- Weight: Weight will be monitored by body mass index, at baseline, week 1, 3, 5 and 7, conclusion and 4 weeks after diet is complete. Body fat measurements via calipers and bioimpedance which will be done at baseline, conclusion and 4 weeks after diet is completed. Vital signs will be monitored weekly.
- Serum:
 - At initiation of diet, conclusion of diet and 4 weeks after diet is complete, fasting labs will be drawn:
 - Clinical Lab: CBC, basic metabolic panel, hemoglobin A1C, triglycerides, insulin, IGF-1, erythrocyte sedimentation rate (ESR), adiponectin, leptin and estradiol
 - Other Serum Markers: IGF-1R, IRS-1, genomic and or proteomic analysis
 - At week 5: a fasting insulin level will be evaluated.

- Psycho-social evaluation: Patients will have psycho-social evaluation using the FACT-B test and the PROMIS cancer fatigue short form at baseline, week 5, conclusion and 4 weeks after conclusion.
- Outcomes: Local recurrence, progression free survival, distant metastases and overall survival will be assessed through patient records after study has been completed.
- Toxicity: acute skin reaction or pain using the National Cancer Institute Common Toxicity Criteria (NCI CTC) version 4.0 scale²² will be assessed. Number of patients experiencing toxicity and time to occurrence of toxicity will be recorded. This toxicity will be compared to historical controls from TJUH who have also been treated for a 6 week course of radiation.

3 Study Design

3.1 General Design

- This is a pilot trial to assess feasibility and toxicity of the dietary intervention during radiation.
- Expected duration of subject participation: approximately 20 weeks, with 10 weeks of diet and follow up
- Section 6.1 outlines the specific trial periods.

3.2 Primary Study Endpoints

Objective: Investigate the feasibility of a clinical trial administering ionizing radiation with concurrent CR for the treatment of breast cancer. True adherence will be defined as a successful reduction of 25% of total calories based on diet journals in at least 80% of the logged events. Acute skin toxicity as defined by the National Cancer Institute Common Toxicity Criteria (NCI CTCv.4 for skin reaction, pain and the occurrence of moist desquamation) will be followed to ensure noninferiority as compared with historical controls.

To obtain baseline caloric intake, patients will keep food diaries for 7 to 10 days. On the basis of these diaries, a caloric intake will be computed for each day. Each patient's baseline (pre-diet) caloric intake will then be the average caloric intake in this pre-diet phase. The target caloric intake during the diet phase will be set to 75% of this baseline average (25% restriction).

The diet phase will be defined as the entire length that a patient is on the calorically restricted diet. This includes a minimum of 2 weeks before the patient starts radiation therapy and a minimum of 2 weeks after completion of radiation therapy. This will guarantee that patients have been on the diet for a minimum of 10 weeks, regardless of whether or not the patients have exceeded the 10 weeks. In the diet phase, patients will also keep daily food diaries. An average daily caloric intake will be computed for each week. If that daily average is more than the restricted target or if there are fewer than 4 diaries during any given week, that week will be considered as non-adherent. Overall adherence with the diet intervention over the entire study will be defined as at least 80% of all logged events meeting the diet restriction target.

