Specific Aim 1: In a clinical trial, will investigate the ability of CR to modulate the effects of radiation in the treatment of early breast cancer. Aim 1a. Adherence will be assessed and is defined for each patient as achieving 25% reduction of her normal caloric intake (weekly average of diet journals), during at least 80% of the days during the intervention. Aim 1b. Acute skin toxicity as defined by the National Cancer Institute Common Toxicity Criteria (NCI CTCv.4 for skin reaction, pain and the occurrence of moist desquamation) will be followed to ensure noninferiority as compared with historical controls. **Specific Aim 2: Investigate measurable changes of patient characteristics along with serum markers from CR to determine a metric for evaluating this treatment in future studies.** Patient characteristics such as weight, vital signs, body fat measurements, psychosocial evaluation and outcomes will be monitored. Additionally, members of the IGF-1R-AKT pathway, and glucose and insulin in the serum, will be assessed to create a molecular signature of response to this therapy.

The innovative use of caloric restriction as a novel therapeutic option has the potential to change the biology of tumors and enhance the clinical benefit of current treatments for breast cancer. If patients are noted to be compliant, we will be able to open a larger study to determine if the combination of radiation and caloric restriction is more efficacious than radiation alone.

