4.5 Early Withdrawal of Subjects

4.5.1 When and How to Withdraw Subjects

Patients will be informed that they have the right to withdraw from the study at any time for any reason, without prejudice to their medical care. The investigator also has the right to withdraw patients from the study for any of the following reasons:

1. Intercurrent illness
2. Occurrence of an unacceptable adverse event such as a Grade ≥ 4 toxicity or $\geq 20\%$ weight
3. Missing more than 3 consecutive days of planned radiation
4. Patient request
5. Protocol violations based on the judgment of PI
6. Non-compliance
7. Administrative reasons
8. Failure to return for follow-up
9. General or specific changes in the patient's condition unacceptable for further treatment in the judgment of the investigator
10. Patients may withdraw from the study voluntarily at any time; however, the Principal Investigator reserves the right to remove patients from the study for any of the following reasons.
11. Radiation toxicity becomes too severe and the patient can no longer tolerate consecutive radiation treatments as determined by treating radiation oncologist.
12. Patients are hospitalized for another condition that is unrelated to breast cancer. Particularly admissions lasting longer than 4 days.
13. Patients develop any of the exclusionary conditions during treatments including: hepatic insufficiency, diabetes, disorders requiring corticosteroid treatment, renal failure or pregnancy.
14. Patients become sexually active and do not wish to use contraception or patients discontinue previous method of contraception and remain sexually active.

At the time of withdrawal, all study procedures outlined for the End of Study visit should be completed. The primary reason for a patient's withdrawal from the study is to be recorded in the source documents.

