4.5.2 Data Collection and Follow-up for Withdrawn Subjects

According to FDA regulations, when a subject withdraws from the study, the data collected on the subject to the point of withdrawal remains part of the study database and may not be removed.

A subject who is withdrawing needs to state whether he/she wishes to provide continued follow-up and further data collection subsequent to withdrawal from the interventional portion of the study.

If a subject withdraws from the interventional portion of the study, but agrees to continued follow-up of associated clinical outcome information as described in the previous bullet, the subject will continue follow up visit and evaluation per the protocol.

If a subject withdraws from the interventional portion of a study and does not consent to continued follow-up of associated clinical outcome information, study data related to the subject collected prior to the subject's withdrawal from the study will included in the study analysis. However, the subject's clinical data will not be used for dose escalation determination.

5 Study Drug/Therapy

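### No rule scores a patient who stops the diet early as non-adherent, so the Phase 1 adherence test leans toward success

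*Combined protocol and SAP*

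**What the plan says.** Section 3.2 defines the window: "The diet phase will be defined as the entire length that a patient is on the calorically restricted diet". It includes at least 2 weeks before and 2 weeks after radiation, and the section adds: "This will guarantee that patients have been on the diet for a minimum of 10 weeks". Each week passes or fails on its average daily intake, and "if there are fewer than 4 diaries during any given week, that week will be considered as non-adherent". The patient-level rule is: "Overall adherence with the diet intervention over the entire study will be defined as at least 80% of all logged events meeting the diet restriction" (that is, the restricted intake goal).

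The Study Summary, section 2.1 and section 5.6 also count logged events. Aim 1a in section 1.2 uses a different denominator: "during at least 80% of the days during the intervention". Section 7.2 sends the primary test to the definition in 3.2.

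Section 4.5.1 lets patients leave at any time. Its reasons for withdrawal include patient request, failure to return and "Non-compliance". For patients who also decline follow-up, section 4.5.2 says that data collected before "withdrawal from the study will included in the study analysis". Section 7.3 restricts analysis to patients with at least 4 diaries per week during the diet phase.

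No section states the adherence score of a patient who stops before the planned end.

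**The concern.** Phase 1 asks whether women can hold a 25% reduction through radiation and for 2 weeks afterwards. Stopping the diet is direct evidence on that question. A window that closes when the patient stops, combined with a denominator of logged events, discards the part of the planned diet that she did not complete. The 10-week minimum in 3.2 describes the schedule. It is not a scoring rule, and 4.5.1 allows a patient to leave before reaching it.

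This is not about sparse logging: the patient in question may log every day until she stops. Section 1.2 makes a larger study depend on patients proving compliant, so an adherence rate that leaves out early stopping could support a study of a diet that fewer women can sustain than the result suggests.

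**Working it through.** **Inputs.** From section 7.1: n = 40, null adherence 60%, assumed true adherence 80%, one-sided exact binomial test, alpha 0.05, stated power 83%. From 3.2: the weekly scoring rule and the 80% threshold. From 7.3: the 4-diary condition. The documents give no dropout rate, so the number of early stoppers is an assumption, varied over 2, 4 and 6 of 40 (5%, 10%, 15%).

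**Step 1: the plan's own figure.** Find the smallest r with P(X ≥ r | n = 40, p = 0.60) ≤ 0.05.
- r = 29 gives 0.0709, which is too large.
- r = 30 gives 0.0352, so success needs 30 of 40.
- Power is P(X ≥ 30 | 40, 0.80) = 0.839, in line with the stated 83%.

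The power statement is sound. The problem is what counts as an adherent patient.

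**Step 2: one patient.** She is on target in weeks 1 to 4, logs fully, then withdraws.
- Window is her time on diet: 4/4 = 100%, adherent.
- Window is 10 planned weeks, scored under 3.2 alone: 4/10 = 40%, non-adherent. A patient would need at least 8 on-target weeks to pass.
- Window is 10 planned weeks, with 7.3 applied: weeks 5 to 10 have fewer than 4 diaries, so she leaves the analysis set before she can count as a failure.

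**Step 3: one trial.** Take 40 patients with 26 adherent completers and 4 stoppers after an on-target start. One-sided exact p-values against 60%:
- stoppers scored adherent: 30/40, p = 0.035, success;
- stoppers scored non-adherent: 26/40, p = 0.317, failure;
- stoppers excluded: 26/36, p = 0.090, failure.

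**Step 4: chance of declaring success when the true rate is the null.** Let 60% of all 40 adhere for the whole planned diet and a share d stop early.
- All stoppers scored adherent: P(X ≥ 30 | 40, 0.60 + d).
- Half scored adherent: P(X ≥ 30 | 40, 0.60 + d/2).
- Stoppers excluded: n' = 40(1 − d), success rate 0.60/(1 − d), critical value recomputed for n' (29 of 38, 27 of 36, 26 of 34).

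| Stoppers of 40 | All score adherent | Half score adherent | Excluded by 7.3 |
|---|---|---|---|
| 0 | 3.5% | 3.5% | 3.5% |
| 2 | 12.1% (p = 0.65) | 6.8% (p = 0.625) | 6.2% (p = 0.632) |
| 4 | 30.9% (p = 0.70) | 12.1% (p = 0.65) | 19.0% (p = 0.667) |
| 6 | 58.4% (p = 0.75) | 20.1% (p = 0.675) | 29.3% (p = 0.706) |

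Every cell with stoppers exceeds the planned 5%.

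**Step 5: power if stoppers count as failures.** If 80% of continuing patients adhere, the overall rate is 0.80(1 − d), that is 76%, 72% or 68%. P(X ≥ 30 | 40, that rate) is 64%, 41% or 22%, against 84% with no stoppers.

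**The case against.** The strongest reply is that 3.2 can be read the other way. The sentence after the definition ties the phase to radiation plus 2 weeks, the adherence sentence speaks of the whole study, and weeks with too few diaries fail. Taken together, blank weeks after stopping could count as failures, and Aim 1a's day-based denominator points the same way. This reading is plausible. A reader might therefore infer from the window definition alone that the plan settles on scoring quitters as successes. The documents do not support that: they are ambiguous. But the kinder reading does not rescue the endpoint while 7.3 stands, because it removes the same patient. Reading 7.3 as an average helps only partly. The patient in step 2 has 4 × 7 = 28 diaries over 10 weeks, or 2.8 a week, and is still out. One who stops after 6 weeks has 42, or 4.2 a week, and would stay in as a 6/10 failure.

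Three further limits stand.
- A woman who abandons the diet but keeps attending still has diaries collected weekly (6.2.3). Her over-target or thinly logged weeks fail under 3.2. The gap needs withdrawal after a largely on-target start.
- The non-compliance item in 4.5.1 is weak support, since such a patient would usually already have failing weeks.
- The quoted sentence in 4.5.2 covers only patients who refuse follow-up, and including data is not the same as scoring someone adherent.

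Counting withdrawals for intercurrent illness or unrelated hospitalization as diet failures is also a choice, with a bias in the opposite direction. It calls for a sensitivity analysis.

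**Conclusion.** The concern holds as a gap in the endpoint definition. Under the literal reading of 3.2 an early stopper with an on-target start is a success. Under the full-window reading, taking 7.3 to require 4 diaries in every week, she is left out. Neither makes stopping count against feasibility, and both push the Phase 1 test toward success.

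The size depends on an assumed number of stoppers and on how they are scored. With a true rate of 60% and 2, 4 or 6 of 40 stopping, the chance of declaring success is between about 6% and 12%, 12% and 31%, or 20% and 58%. A reader might take 12%, 31% and 58% as the expected error rates. They are the upper case, in which every stopper scores adherent, and the documents give no basis for that share.

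Nor should the result be read as a gate that wrongly opens Phase 2. The Study Summary simply proceeds to the second phase, and section 8.4 has no formal interim stopping analysis. What is at stake is the feasibility conclusion and the larger study that section 1.2 makes depend on it.

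**What to change.** - **Section 3.2:** score each patient over a fixed planned window, from the planning session to 2 weeks after the last planned fraction. Use planned diet weeks as the denominator in place of logged events. Count as non-adherent any week after stopping or withdrawal, and any week with fewer than 4 diaries.
- **Section 7.3:** remove the 4-diaries-per-week condition for the adherence analysis, so that all enrolled patients who start the diet stay in the denominator. Without this, the change to 3.2 has little effect, because 7.3 would remove the stoppers.
- **Study Summary, 1.2 (Aim 1a), 2.1 and 5.6:** align the adherence wording with 3.2.
- **Section 7.2:** add a sensitivity analysis that leaves out withdrawals unrelated to the diet.
- **Section 7.1:** state that the 80% assumption refers to all patients who start the diet.

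The cost is a handful of sentences across these sections and no new data. The adherence estimate will be less favourable, and some unrelated withdrawals will count as failures in the main analysis. If 80% describes only continuing patients, power drops to about 64%, 41% or 22% with 2, 4 or 6 stoppers, which is why 7.1 must say whom the 80% describes. The change concerns scoring and analysis only, not how patients are treated or withdrawn.
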